13. STATISTICAL METHODS

13.1.1 Methods of Analysis for Repeated Continuous Endpoints

Treatment group comparisons on endpoints that are continuous variables assessed repeatedly will be done using MMRM with change from baseline as the dependent variable; nominal visit (time), treatment group, and treatment-by-time interaction as fixed effects; baseline observation as a fixed-effect covariate (if applicable); and correlated errors within subject. Site will be included as a random effect if doing so appreciably affects treatment effect estimates. Covariance estimation will be done using restricted maximum likelihood. Error degrees of freedom will be calculated using the Kenward-Rogers approximation. Unstructured covariance for the residuals (R matrix) will initially be specified but other covariance structures may be explored by examining the R matrix and using goodness-of-fit measures (e.g., Akaike's Information Criterion). If a structured covariance is used, the sandwich estimator will be used for SEs and error degrees of

Confidential Page 22 of 33

freedom will be calculated using the between-within method. Model-based LS means will be reported for each treatment group, along with CIs and p-values for treatment group comparisons, for each nominal visit. A p-value for treatment group comparison over all visits will only be reported if there does not appear to be a treatment-by-time interaction, either based on the interaction p-value or by a descriptive examination of the data, and the term for treatment-by-time interaction will not be included in the model.

Model assumptions will be evaluated using diagnostic tools such as Q-Q and scatter plots of residuals, and sensitivity analyses using alternative methods (e.g., rank-based, GLM at individual time points) will be considered if there appear to be substantial deviations from model assumptions. Outlier assessment will be done using visual inspection (e.g., box-and-whisker plots) and potential outliers will be investigated for data entry accuracy and biological consistency. If unexplainable outliers are present, a sensitivity analysis may be done excluding the outliers to assess their effect on the analysis conclusion.

Within-group analyses of changes from baseline on endpoints that are continuous variables assessed repeatedly will also be done using MMRM with observed value as the dependent variable, nominal visit (time) as a fixed effect, and correlated errors within subject. Model-based means will be reported for each treatment group, along with CIs and p-values, for each post-baseline nominal visit.

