12.1 Efficacy Parameters

12.1.1 VAS and NRS-11

Ear pain will be measured by VAS and NRS-11. Scores will be collected for each ear at Baseline and 10, 20, 30, and 60 minutes post dose.

The VAS consists of a 100 mm line anchored by 2 extremes of pain, with the left anchor representing "no pain" and the right anchor representing "worse pain." Study Participants mark the line where their pain is best represented between the 2 anchors. The VAS score is the distance from the left anchor to the Study Participant's mark.

Confidential Page 18 of 33

NRS-11 pain scores range from 0 to 10, with 0 representing "no pain" and 10 representing the "worst pain possible." NRS-11 \geq 5 reflects moderate to severe pain and is an inclusion criterion.

Listings will show observed values and absolute changes from baseline for each ear separately, for the sum over both ears, and for the maximum score across both ears. For both VAS and NRS-11, decreasing change scores from baseline indicate improvement and this will be footnoted in TFLs.

Endpoints

The following endpoints will be calculated for both VAS and NRS-11, unless otherwise indicated, using (a) the sum of scores over both ears, and (b) the maximum score across both ears:

- PID_{t_i} where i = 1 to 4 and t_1 , t_2 , t_3 , $t_4 = 10$, 20, 30, and 60 minutes post dose, respectively, and PID_{t_i} = score at time t_i score at baseline (ie, change from baseline).
- SPID_t I defined as

$$SPID_{t_{-}I} = \sum_{i=1}^{I} PID_{t_{-}i} (t_i - t_{i-1})$$

where I = 1 to 4, t_0 is baseline, and t_1 , t_2 , t_3 , t_4 are time points 10, 20, 30, 60 minutes post dose, respectively. For example, SPID₂ is the sum of changes from baseline at 10 and 20 minutes post baseline weighted by time (in minutes) since the previous measurement.

- Percent change from baseline (per inclusion criteria, baseline VAS and NRS-11 are unlikely to be 0).
- Presence of any pain, defined as score > 0 at 10, 20, 30, and 60 minutes post dose.
- Improvement categorized as "worsening" (positive change score), "no change" (0 change score), "improvement" (negative change score) at 10, 20, 30, and 60 minutes post dose.

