- Time to pain relief defined as time point (10, 20, 30, 60 minutes post dose or no pain relief) at which relief was achieved, where "relief" is defined as score < 5 for NRS-11 and at least a 30 mm decrease from baseline for VAS. In the unlikely event that a Study Participant has a baseline VAS less than 30 mm, they will be excluded from the VAS analysis of time to pain relief.
- Response, defined as a 25%, 50%, and 75% reduction in score, at 10, 20, 30, and 60 minutes post dose.

Summaries and Analyses (see Section 13)

• PID_{t_i} will be analyzed using mixed model for repeated measures (MMRM). A summary table will include least-squares (LS) means and standard errors (SEs) for each treatment group and the estimate of treatment group difference with 80, 90, and 95% confidence intervals (CIs) for the difference and associated p-values. LS means and SEs will also be graphically displayed using a line chart. In addition, 80, 90, and 95% CIs and associated p-values for within-group mean changes from baseline will be included in the summary table.

Confidential Page 19 of 33

- SPID_{t_I} will be analyzed using mixed model for repeated measures (MMRM). A summary table will include least-squares (LS) means and standard errors (SEs) for each treatment group and the estimate of treatment group difference with 80, 90, and 95% confidence intervals (CIs) for the difference and associated p-values. LS means and SEs will also be graphically displayed using a line chart. In addition, 80, 90, and 95% CIs and associated p-values for within-group mean changes from baseline will be included in the summary table.
- Response will be analyzed using general estimating equations (GEE). A summary table will include LS means and SEs for each treatment group and the estimate of treatment group difference with 80, 90, and 95% CIs for the difference and associated p-values. Crude response rates will be graphically displayed using a bar chart.
- Percent change from baseline, presence of pain, improvement category, and time to pain relief will be summarized in tables but will not be subjected to statistical inference.

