12.1.2 PGIC and CGI-I

PGIC scores will be collected at 10, 20, 30, and 60 minutes post dose. Study Participants will be asked "How have your symptoms been since you received the study treatment?" Scores range from 1 to 7 with 1 = very much improved, 2 = much improved, 3 = minimally improved, 4 = no change, 5 = minimally worse, 6 = much worse, and 7 = very much worse.

CGI-I score will be collected at 60 minutes post dose. Physician investigators will be asked "How has the subject's symptoms been since they received the study treatment?" The score range and meaning of each score are the same as for PGIC described above.

Listings will show observed values. Lower scores indicate better symptom status and this will be footnoted in TFLs.

Endpoints

The following endpoints will be calculated for both PGIC and CGI-I at each time point collected:

- Observed value.
- Response, defined as much improved or very much improved.

Summaries and Analyses (see Section 13)

- PGIC observed value will be analyzed using MMRM with baseline NRS-11 as a covariate. A summary table will include LS means and SEs for each treatment group and the estimate of treatment group difference with 80, 90, and 95% CIs for the difference and associated p-values. LS means and SEs will also be graphically displayed using a line chart. Frequency distributions of observed responses will also be summarized.
- CGI-I observed valued will be analyzed using GLM with baseline NRS-11 as a covariate. A summary table will include LS means and SEs for each treatment group and the estimate of treatment group difference with 80, 90, and 95% CIs for the difference and associated p-values. Frequency distributions of observed responses will also be summarized.
- Response will be analyzed using GEE with baseline NRS-11 as a covariate (if convergence can be achieved). A summary table will include LS means and SEs for each treatment group

Confidential Page 20 of 33

and the estimate of treatment group difference with 80, 90, and 95% CIs for the difference and associated p-values.

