13.1.2 Method of Analysis for Non-Repeated Continuous Endpoints

Treatment group comparisons on endpoints that are continuous variables not assessed repeatedly will be done using GLM with change from baseline as the dependent variable, treatment group as an independent variable, and baseline observation as a covariate (if applicable). Model-based LS means will be reported for each treatment group, along with CIs and p-values for treatment group comparisons.

Model assumptions will be evaluated using diagnostic tools such as Q-Q and scatter plots of residuals, and sensitivity analyses using alternative methods (e.g., rank-based) will be considered if there appear to be substantial deviations from model assumptions. Outlier assessment will be done using visual inspection (e.g., box-and-whisker plots) and potential outliers will be investigated for data entry accuracy and biological consistency. If unexplainable outliers are present, a sensitivity analysis may be done excluding the outliers to assess their effect on the analysis conclusion.

A random effects linear model will be used to assess the impact of site, as a random effect, on treatment effect estimates. If the effect is appreciable, a random effects model will be used in place of GLM.

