13.1.4 Missing Observations

One of the assumptions of MMRM is that missing observations are missing at random (MAR), i.e., missingness is unrelated to the variable for which the observation is missing but can be related to another variable on which data have been collected. This assumption is not testable. However, given the short time frame of data collection for exploratory endpoints (60 minutes), it is unlikely that data will be missing not at random (MNAR). It is also unlikely that a substantial proportion (> 10%) of Study Participants will have missing observations. Therefore, the MAR assumption will be considered adequate to address any missing observations for variables analyzed using MMRM.

GEE assumes missing observations are missing completely at random (MCAR); i.e., missingness is independent of all other information whether it was collected or not. Again, due to the short time frame of data collection, this assumption will be considered adequate.

If > 10% of Study Participants have missing observations for a given endpoint, multiple imputation may be used for sensitivity analyses. Under an MNAR model, imputations will be based only on subjects randomized to placebo. The imputation method will be fully conditional specification (FCS) regression with 25 imputations. The imputer's model will include observed values at each time point included in the analysis, including baseline if applicable.

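### One shared baseline coefficient for the four cumulative SPIDs leaves SPID over 60 minutes almost unadjusted for baseline pain

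*SAP*

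**What the plan says.** SAP section 12.1.1 builds SPID cumulatively. In its own example, SPID at the second time point "is the sum of changes from baseline at 10 and 20 minutes post baseline weighted by time (in minutes) since the previous measurement". Four SPIDs result, with increments 10·PID10, 10·PID20, 10·PID30 and 30·PID60. They are calculated for the VAS and the NRS-11, each on "a) the sum of scores over both ears, and (b) the maximum score across both ears". The same section sends SPID to an MMRM and reports LS means, treatment differences, 80, 90 and 95% CIs, and p-values.

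SAP section 13.1.1 specifies the MMRM. Time, treatment and treatment-by-time are fixed effects, with "baseline observation as a fixed-effect covariate (if applicable); and correlated errors within subject". Estimation is by REML, starting from an unstructured covariance. Neither document contains a baseline-by-time term.

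Two other places bear on this:

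- Protocol section 5.2.6.1 analysed SPID by a linear model with its own baseline pain term. SAP section 15 records the move to MMRM, the change for site and the change in missing-data handling. It does not mention baseline adjustment.
- For PGIC, which has no pre-dose value, SAP section 12.1.2 names a covariate: "PGIC observed value will be analyzed using MMRM with baseline NRS-11 as a covariate". SPID has no pre-dose value either, and none is named for it.

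**The concern.** A main-effect baseline term is reasonable for PID, whose baseline slopes are on a common scale at every time. Cumulative SPIDs are different: their slopes grow with time by construction, so a single coefficient is wrong for at least three of the four. The question is where the fitted coefficient lands, and whether SPID over 60 minutes (SPID60) still gets a useful adjustment.

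If it does not, SPID60 loses the precision that adjustment brings, and chance baseline differences pass straight into the treatment estimate. With 12 per arm such differences are to be expected. The two-ear sum is most exposed, because it mixes unilateral and bilateral disease and so has a wide baseline spread.

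**Working it through.** **Inputs.** From the documents: weights 10, 10, 10 and 30 minutes (SAP 12.1.1); 12 per arm (protocol 5.2.1); REML and unstructured covariance (SAP 13.1.1); two-sided testing starting at 0.20 (SAP 8.3). The documents give no SD, correlation, baseline slope or bilateral share, and no power figure to reproduce. Assumed: PID = b × baseline + error, with b from -0.1 to -0.5; equal error correlation r from 0.3 to 0.9; error SD 2, or 2 × √2 = 2.83 for two independent ears; baseline SD 1.5 for the worst ear. For the sum, take mean 7 and SD 1.5 per affected ear, 0 in the other ear, and bilateral share p. The baseline variance is then 2.25(1 + p) + 49p(1 - p):

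- p = 0.10: 2.475 + 4.41 = 6.885, SD 2.6
- p = 0.25: 2.8125 + 9.1875 = 12.0, SD 3.5

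SDs of 2.7 and 3.5 were used.

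**Slopes needed.** Adding the weights gives 10b, 20b, 30b and 60b. At b = -0.5 these are -5, -10, -15 and -30.

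**Slope obtained.** An unstructured likelihood is unchanged when the four SPIDs are re-expressed as their increments. One coefficient c shared by the SPIDs is therefore the same as slopes (c, 0, 0, 0) on the increments. With complete data, the estimate of c is the partial slope of 10·PID10 on baseline, given treatment and the three later increments. Under equal correlation, each later PID enters with weight r/(1 + 2r), so

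c = 10b × [1 - 3r/(1 + 2r)] = 10b(1 - r)/(1 + 2r), and c/(60b) = (1 - r)/[6(1 + 2r)].

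| r | c at b = -0.5 | needed at 60 min | share |
|---|---|---|---|
| 0.3 | -5 × 0.7/1.6 = -2.19 | -30 | 7.3% |
| 0.5 | -5 × 0.5/2.0 = -1.25 | -30 | 4.2% |
| 0.7 | -5 × 0.3/2.4 = -0.63 | -30 | 2.1% |
| 0.9 | -5 × 0.1/2.8 = -0.18 | -30 | 0.6% |

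Simulated mean slopes agree: -0.1 to -2.3 at b = -0.5; -0.1 to -1.4 where -18 is needed (b = -0.3); -0.02 to -0.5 where -6 is needed (b = -0.1). With serial rather than equal correlation the share was about -5% to +5%, apart from two cases in which the 60-minute slope was itself small.

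**Effect on SPID60.** The treatment estimate is the raw mean difference minus c times the baseline gap. The table gives its variance relative to ANCOVA (60 settings, 4,000 runs each; ranges are over r).

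| Score | Baseline SD | Error SD | b = -0.1 | b = -0.3 | b = -0.5 |
|---|---|---|---|---|---|
| Worst ear | 1.5 | 2 | 3-4% smaller | 1-5% larger | 9-17% larger |
| Sum | 2.7 | 2.83 | 4-5% smaller | 1-8% larger | 16-29% larger |
| Sum | 2.7 | 2 | 1-3% smaller | 11-20% larger | 38-63% larger |
| Sum | 3.5 | 2.83 | 2-3% smaller | 9-18% larger | 29-54% larger |
| Sum | 3.5 | 2 | 0-3% smaller | 19-37% larger | 70-111% larger |

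Example (sum, SDs 3.5 and 2.83, r = 0.7, b = -0.5): the SD of the SPID60 difference is 75.3 against 63.9, and (75.3/63.9)² = 1.39.

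**A smaller error SD for one ear.** Take baseline and post-dose SDs of 1.5, baseline-to-post correlation 0.5 and post-to-post correlation 0.7. Then b = -0.5, error SD = 1.5 × √0.75 = 1.30, and error correlation = (0.7 - 0.25)/0.75 = 0.6. The shared slope is -5 × 0.4/2.2 = -0.91, or 3.0% of -30. The simulated SD of the SPID60 difference was 32.8, against 33.0 unadjusted and 27.7 for ANCOVA. For an assumed constant 1-point benefit (60 point-minutes) at two-sided 0.20, power ≈ Φ(60/SD - 1.28), which is about 71% against 81%.

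**Chance imbalance.** One SE of the baseline gap is SD × √(2/12): 0.61 points for the worst ear and 1.43 for the sum at SD 3.5. Multiplied by 60 × |b|, the uncorrected shift is 4-18 or 9-43 point-minutes for b from -0.1 to -0.5, against the same 60 point-minutes.

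**Checks.** The closed form matched direct REML fits to 10⁻⁷ in 30 data sets. With complete data, the baseline-by-time model gave the ANCOVA estimate of SPID60 (largest difference 3 × 10⁻¹¹). Type I error at nominal 20% was 18.9-21.6% for the one-slope model and 19.0-21.3% for ANCOVA.

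**The case against.** The strongest reply concerns size and stakes. At b = -0.1 the planned model is as good as ANCOVA or slightly better. For the worst ear with error SD 2 and r = 0.7, simulated power for a 1-point effect at two-sided 0.20 barely moves: 51.4% against 52.0% at b = -0.3, and 49.0% against 51.1% at b = -0.5. A clear loss needs the sum with a wide baseline and small error: 39.7% against 53.1% at baseline SD 3.5, error SD 2 and b = -0.5. No document figure says which setting applies. SPID is one of many exploratory endpoints, the primary endpoints are safety, and the adjusted PID analysis of the same data is planned at all four times. All of this stands, and it limits the weight of the point.

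The wording can also be defended. SAP section 8.6 defines a baseline observation per parameter, so baseline VAS or NRS-11 on the matching score is a natural reading. That may well be intended. But SPID60 is almost unadjusted whether the text means one shared slope or no covariate.

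The flexibility in section 13.1.1 does not close the gap. Other covariance structures are optional, and an equal-variance structure would supply only about half the needed slope (-15 of -30 in the error-SD-1.3 case). The fallback, "GLM at individual time points) will be considered if there appear to be substantial deviations from model assumptions", is also discretionary. The planned PID differences, weighted 10, 10, 10 and 30, do rebuild an adjusted SPID60 point estimate, but the planned output gives no CI or p-value for that combination.

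**Conclusion.** The concern holds. That the shared slope is near zero follows from the SAP's SPID definition, the missing baseline-by-time term and the unstructured covariance. It does not depend on the assumed SDs.

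The consequence does depend on them. The loss is nil if baseline pain hardly predicts change. For the worst ear it is small at error SD 2, but about 28-44% in variance at error SD 1.3 with b = -0.5. For the two-ear sum it can be large when baseline predicts change, and the 70-111% figure is the extreme corner of the range examined. The treatment estimate is not biased on average and type I error is not inflated. PID is unaffected if its baseline slope is constant over time. The safety objective is untouched. This is a cheap correction that should be made to an exploratory analysis, not a threat to the trial's conclusions.

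**What to change.** In SAP section 13.1.1, for SPID, drop the *if applicable* qualifier. Name baseline pain on the matching scale (VAS or NRS-11, sum or maximum) as the covariate, and add a baseline-by-time interaction. With complete data this reproduces ANCOVA for SPID60 and restores the baseline adjustment of the protocol's SPID model. It is a change of wording only, with no new data. It uses three extra parameters, costs 0-5% in variance if the baseline slope is weak (b = -0.1), and leaves section 13.1.4 as it is, where "the MAR assumption will be considered adequate to address any missing observations for variables analyzed using MMRM".

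The alternative is a single ANCOVA of SPID60 under section 13.1.2. The covariate must be named there too, since that section carries the same qualifier. Because LOCF has been removed, this version drops any subject with a missing PID unless the value is imputed. If about 10% lack the 60-minute value (assumed, missing completely at random), its variance is 5-13% larger than that of the baseline-by-time MMRM. The MMRM form is therefore preferable.

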5.2.6 Efficacy Analyses

5.2.6.1 Exploratory Analysis

Pain Intensity Difference (PID) & Sum Pain Intensity Difference (SPID) will be calculated as follows:

• PID will be calculated as:

$$PID_t = PI_t - PI_{Baseline}$$

Where t is the post-dose assessment timepoint

Where baseline is the predose assessment timepoint

• SPID will be calculated as:

$$SPID_{ti-ti+n} = \sum_{ti}^{ti+n} (PID_i) * (t_{i+1} - t_i)$$

Where PID_i is the pain intensity difference score calculated at each post-dose timepoint

Where t_i is the scheduled assessment time

Analyses for Continuous Data

PID (change from Baseline) will be computed for each post-dose assessment timepoint (10, 20, 30, and 60 min). Data will be analysed using a longitudinal mixed model for repeated measures with fixed effects for treatment, time, treatment-by-time interaction, study site, and baseline pain score. Subject will be the random effect. Treatment differences from control (placebo) will be estimated from the Least Squares Means (LSM) from the analysis model along with 80% confidence intervals (CIs) and associated 2-sided p-values. If significance is found using 80% CIs, 90% and 95% CIs will also be tested. Only observed cases will be included in the PID computations. Graphical displays of the LSM change from Baseline will also be provided by treatment.

Descriptive summaries for each PID timepoint will be provided by treatment along with the model output for test differences in the LSM. PID analyses will be conducted for both NRS-11 and VAS pain scales.

SPID will be analysed using a linear model analysis of variance (ANOVA) with fixed effects for treatment, site, and baseline pain score. Treatment differences from control (placebo) are estimated using the LSM from the analysis model along with 80% CIs and associated 2-sided p-values. If significance is found using 80% CIs, 90% and 95% CIs will also be tested. SPID analyses will be conducted for both NRS-11 and VAS pain scales. Missing data will be handled using the Last Observation Carried Forward imputation method.

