8.3 General Analysis Conventions

Categorical variables will be summarized using frequencies and percentages. Percentages will be reported to one decimal place. Unless otherwise noted in Section 11, categorical variables will be analyzed using chi square tests of association or, if any contingency table cell has less than 5 subjects, Fisher's exact test.

Continuous variables will be summarized using descriptive statistics (e.g., n, mean, standard deviation, least-squares mean with standard error, distribution percentiles, range). The number of decimal places for minimums and maximums will be the same as the original data. The number of decimal places for means, medians, and interquartile ranges will be the same as the original data plus one. The number of decimal places for measures of variance will be the same as the original data plus two. Unless otherwise noted in Section 11, continuous variables will be analyzed using t-tests or a non-parametric alternative.

Data with qualifiers (e.g., "<") will be listed with but summarized without the qualifier.

P-values will be presented in summary tables to two decimal places if > 0.01, to three places if < 0.01 but > 0.001, and to four places if < 0.001 but > 0.0001. However, p-values > 0.045 but < 0.055 will also be presented to three decimal places. P-values < 0.0001 will be presented as "< 0.0001."

Statistical tests will be two-sided and tested at the 0.20, 0.10, and 0.05 significance levels in a hierarchical manner.

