13.1.3 Method of Analysis for Repeated Binary Endpoints

Treatment group comparisons on binary endpoints assessed repeatedly will be done using GEE with nominal visit (time) and treatment group as main effects, treatment-by-time as an interaction term, an appropriate baseline value as a covariate (if applicable); and correlated errors within subject.

Confidential Page 23 of 33

The working correlation structure will initially be specified as unstructured but other structures may be explored by examining the covariance matrix and using goodness-of-fit measures (e.g., Quasilikelihood under the Independence model Criterion). P-values for treatment group comparisons will be reported for each nominal visit. A p-value for treatment group comparison over all visits will only be reported if there does not appear to be a treatment-by-time interaction, either based on the interaction p-value or by a descriptive examination of the data, and the term for treatment-by-time interaction will not be included in the model.

Alternative approaches for the analysis of binary endpoints, such as random-effects models (including site as a random effect if doing so appreciably affects treatment effect estimates), chi squares tests of association or Fisher's exact tests, may be considered.

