13.1.5 Multiplicity

There will be no adjustments for type 1 error inflation due to multiplicity.

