15. CHANGES FROM THE PROTOCOL

Confidential Page 24 of 33

| Protocol | Change |
|--|---|
| Primary endpoints: AEs recorded over 60 min post dose and at Day 7 | Incidence, seriousness, severity, and relatedness to study treatment of adverse events (AEs) recorded over 60 minutes post dose and at Day 7 |
| Change from Baseline in the VAS and the NRS-11 listed as an exploratory endpoint. AOM symptoms and Device Experience Questionnaire were included as "exploratory objectives" but were not stated as "exploratory endpoints." | Change from Baseline removed as an exploratory endpoint (same as PID). The following endpoints were added as exploratory endpoints: • Presence of AOM symptoms • Response on Device Experience Questionnaire – Subject • Response on Device Experience Questionnaire – Study Staff Administering Treatment |
| Data listings will be sorted by treatment, subject number, and time point unless otherwise noted. Site included as a fixed effect in mixed models. Only observed cases will be included in the PID computations. | Listingswill be ordered by unique subject identifier, parameter, date, data collection time if applicable, nominal study visit, and analysis visit window if applicable. Site included as a random effect if doing so appreciably affects treatment effect estimates. If > 10% of Study Participants have missing observations for a given endpoint, multiple |
| SPID will be analysed using a linear model analysis of variance (ANOVA) with fixed effects for treatment, site, and baseline pain score. Missing data will be handled using the Last Observation Carried Forward imputation method. | imputation may be used for sensitivity analyses. SPID will be analyzed using MMRM. Site will be included as a random effect if doing so appreciably affects treatment effect estimates. If > 10% of Study Participants have missing observations for a given endpoint, multiple imputation may be used for sensitivity analyses. |
| For ear pain: Hodges-Lehmann point estimate and 80% 2-sided CI for the median of treatment effect differences between active and placebo will be provided. Statistical comparisons of ear pain, as measured by the VAS and the NRS-11, | There is no separate analysis for "ear pain"; covered by analyses of VAS and NRS-11. |

Confidential Page 25 of 33

| 1 | |
|---|---|
| between the treatments at 60 min post dose | |
| will be performed using an ANOVA model. | |
| Ear pain responder analysis: | Based on \geq 25%, 50% and 75% reduction |
| | |

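### Site enters each efficacy model only if it "appreciably" moves the unblinded treatment estimate, with no threshold and no duty to report both models

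*SAP*

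**What the plan says.** For repeated continuous endpoints (PID, SPID, PGIC), SAP 13.1.1 says: "Site will be included as a random effect if doing so appreciably affects treatment effect estimates". For non-repeated continuous endpoints (CGI-I), SAP 13.1.2 says: "A random effects linear model will be used to assess the impact of site, as a random effect, on treatment effect estimates", and then: "If the effect is appreciable, a random effects model will be used in place of GLM". SAP 13.1.3 has no site term in the main GEE model, but mentions random-effects models among the alternatives that may be considered, "including site as a random effect if doing so appreciably affects treatment effect estimates".

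Protocol 5.2.6.1 specified the PID model with "fixed effects for treatment, time, treatment-by-time interaction, study site, and baseline pain score", and also listed site without condition for SPID, PGIC and CGI-I. SAP Section 15 records the replacement: "Site included as a random effect if doing so appreciably affects treatment effect estimates". It gives neither a reason nor a threshold. Protocol 5.2 lets the SAP prevail where the two differ, so the SAP wording is operative.

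On testing, SAP 8.3 says: "Statistical tests will be two-sided and tested at the 0.20, 0.10, and 0.05 significance levels in a hierarchical manner". SAP 13.1.5 adds: "There will be no adjustments for type 1 error inflation due to multiplicity".

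**The concern.** The condition refers to the quantity the model is meant to estimate. To apply it, the analyst must fit both models with treatment codes attached and compare the two treatment effects. SAP 14.1 places the only planned analysis after database lock, and no blinded model-selection step is described.

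The rule also cannot be applied uniquely. *Appreciably* has no numerical meaning. The SAP does not say which time point, scale or ear summary supplies the estimate to be compared, so site could enter one endpoint's model and not the next. The reported interval and p-value would take no account of the choice.

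The design gives site room to matter. SAP 6.1 specifies fixed blocks of 4 and states no stratification by site. Protocol 6.8 calls the trial multicentre, and about 24 subjects are planned, so the arms may be unbalanced within sites. The SAP preface says the planned analyses are meant for regulatory submissions and/or manuscripts.

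**Working it through.** **1. What can be checked.** The documents give no number of sites, site variance or threshold, and Protocol 5.2.1 gives 24 subjects without power, effect size or SD. There is no planned figure to reproduce. What follows rests on stated assumptions.

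**2. How many estimates the rule touches.** From SAP 12.1.1, 2 measures (PID, SPID) × 2 scales (VAS, NRS-11) × 2 ear summaries (sum, maximum) = 8 MMRMs. At 4 time points each, that is 8 × 4 = 32 treatment estimates, before PGIC and CGI-I.

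**3. Null simulation.**
- From the documents: 24 subjects, 1:1, blocks of 4 not stratified by site, baseline covariate, two-sided 0.20.
- Assumed: 3 or 6 sites; site share of baseline-adjusted variance (ICC) 0, 0.1 or 0.3; *appreciable* read as a relative change in the treatment estimate above 10% or 20%.
- Simplified: one time point; REML random site intercept tested on 24 − 3 = 21 df, not the Kenward-Roger df the SAP names.
- Size: 4,000 trials per scenario. The 95% simulation error is about 1.96 × √(0.20 × 0.80 / 4000) = 0.012.

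Proportion of null trials with p < 0.20:

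| Sites, ICC | No site | Random site | Fixed site | 10% rule | 20% rule | Smaller p kept |
|---|---|---|---|---|---|---|
| 3, 0 | 0.202 | 0.214 | 0.200 | 0.211 | 0.210 | 0.219 |
| 3, 0.1 | 0.192 | 0.207 | 0.196 | 0.201 | 0.201 | 0.221 |
| 3, 0.3 | 0.199 | 0.212 | 0.203 | 0.206 | 0.202 | 0.248 |
| 6, 0 | 0.194 | 0.210 | 0.198 | 0.210 | 0.208 | 0.218 |
| 6, 0.1 | 0.206 | 0.227 | 0.204 | 0.220 | 0.217 | 0.243 |
| 6, 0.3 | 0.200 | 0.213 | 0.198 | 0.206 | 0.204 | 0.255 |

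How often site is added, and how often the random-site and no-site models disagree on p < 0.20:

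| Sites, ICC | Added, 10% rule | Added, 20% rule | Models disagree |
|---|---|---|---|
| 3, 0 | 0.219 | 0.165 | 0.022 |
| 3, 0.1 | 0.401 | 0.302 | 0.043 |
| 3, 0.3 | 0.604 | 0.498 | 0.085 |
| 6, 0 | 0.258 | 0.186 | 0.031 |
| 6, 0.1 | 0.406 | 0.308 | 0.053 |
| 6, 0.3 | 0.644 | 0.533 | 0.098 |

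**4. Consistency check.** The chance that at least one model rejects equals half the sum of the two rejection rates and the disagreement rate. For 6 sites and ICC 0.3: (0.200 + 0.213 + 0.098) / 2 = 0.2555, against 0.255 in the table.

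**5. Share due to selection.** Smaller-p minus always-random is 0.219 − 0.214 = 0.005 at the low end (3 sites, ICC 0) and 0.255 − 0.213 = 0.042 at the high end (6 sites, ICC 0.3). The mechanical rules (0.201 to 0.220) do not exceed always-random (0.207 to 0.227).

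**6. Other settings.** A separate run with 4 or 8 sites (1,500 null trials per scenario) gave disagreement in 3 to 8% of trials and 0.23 to 0.25 when the smaller p was kept.

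**7. With a real effect.** At 12 per arm, two-sided 0.20 and 80% power, the detectable difference is (1.2816 + 0.8416) × √(2/12) = 0.87 SD. In a run with 3 or 6 sites and site variance 0 or 0.3, the 10% trigger fired in 22 to 56% of null trials but in 12 to 39% at 0.87 SD. Null rates are high partly because a relative change is measured against an estimate near zero.

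**The case against.** The SAP's criterion is a change in the estimate, not a p-value. An unchanged estimate gives no ground for adding site, so the rule is not a licence to pick the better result. Sections 13.1.1 and 13.1.2 have a default, the model without site. The change is disclosed in Section 15. A fixed threshold applied mechanically does no visible harm, and the inflated figure requires a choice that the SAP does not prescribe. The affected endpoints are exploratory, tested at 0.20 without multiplicity adjustment, while the primary endpoints are safety summaries that do not use these models. In 13.1.3 site appears only among optional alternatives.

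Most of this stands and limits the size of the point. It does not remove the defect: the default is overridden by an undefined word applied to the unblinded treatment estimate, and nothing requires the unused model to be shown.

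Three stronger readings are tempting, and the documents do not support them. A reader might infer that either model can always be defended after seeing both p-values, but the criterion bars this when the estimate hardly moves, and the models reach the same verdict at 0.20 in roughly 90 to 98% of simulated null trials. A reader might infer that endpoints can no longer be compared; different models make comparison harder, not impossible. A reader might infer that a random site term in every model would control error better; the simulation does not show that, and the slight excess over 0.20 in the random-site column goes with its naive df, whereas the SAP specifies Kenward-Roger.

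**Conclusion.** The point holds as a pre-specification defect of modest size. The SAP replaced an unconditional site term with a rule that depends on the treatment estimate, has no threshold or reference estimate, and can give different models across endpoints, scales and ear summaries.

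Under the assumed inputs, the choice alters the verdict at 0.20 in about 2 to 10% of null trials per estimate. It raises type I error to about 0.21 to 0.25 only if the more favourable model is reported. Moving the threshold from 10% to 20% shifts the share of null trials in which site is added from 22–64% to 17–53%, so the undefined word itself decides some models.

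These figures depend on the assumed number of sites, site variance and threshold, and on a single time point without Kenward-Roger df. They show direction and order of size, not a prediction for this trial. No safety conclusion is affected.

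**What to change.** Before unblinding, name one site handling for the main analysis of all continuous endpoints. Either of these would do:

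- an unconditional random site intercept with Kenward-Roger df, with a fallback for non-convergence or zero estimated site variance that does not consult the treatment estimate;
- the protocol's fixed site effect.

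Report the alternative as a sensitivity analysis for every endpoint. Delete the condition on the treatment estimate in SAP 13.1.1 to 13.1.3 and Section 15. In 13.1.3, say how site is handled in any alternative binary model that is used.

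The change is to SAP wording only; no data collection or conduct is touched. The price is some flexibility and a small loss of df, larger with fixed site if there are many small sites. In a single-time-point model with treatment and baseline, 6 fixed sites would take residual df from 21 to 21 − 5 = 16, and 8 sites to 21 − 7 = 14. The zero-variance fallback is itself data-dependent, but not on the treatment effect, which is the feature that needs removing.
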